	15 SEP 2015
	09 OCT 2015
Final	04 JAN 2016
#1	04 AUG 2016

1.0 SYNOPSIS

Name of Sponsor/Institute: Tufts Medical Center, Inc. Funding grant provided by the National Heart, Lung and Blood Institute, National Institutes of Health (NHLBI/NIH)
	

Name of Investigational Product: PZ-128
	
Name of Active Ingredient: PZ-128

Title of Study: A Multi-center, Randomized, Double-Blind, Placebo-Controlled Study to Evaluate the Safety of PZ-128 in Subjects Undergoing Non-Emergent Percutaneous Coronary Intervention Thrombin Receptor Inhibitory Pepducin in PCI (TRIP-PCI) (Protocol No. TMC-PZ128-02)
	

Study Sites: Inova Heart and Vascular Institute, Inova Fairfax Hospital, Falls Church, VA Tufts Medical Center, Boston, MA UMass Memorial Medical Center, Worcester, MA
	

Projected Study Timelines: Actual date first subject enrolled: 27 May 2016 Estimated date last subject enrolled: December 2018 Estimated date last subject completed: March 2019
	
Clinical Phase: 2

Indication: Non-emergent percutaneous coronary intervention (PCI)
	

Primary Objective: The primary objective is to evaluate the safety of single dose PZ-128, in addition to the standard of care, with respect to the incidence of major and minor bleeding events, as assessed by the TIMI (Thrombolysis in Myocardial Infarction) classification, in subjects undergoing non-emergent PCI or non-emergent cardiac catheterization with the intent to perform PCI.
 
Key Secondary Objective: The key secondary objective is to evaluate the potential clinical benefit of PZ-128 with respect to the composite endpoint of major adverse cardiac events (MACE) - any of cardiovascular death, non-fatal myocardial infarction (MI), non-fatal stroke, recurrent ischemia requiring hospitalization or urgent coronary revascularization.
 
Other Secondary Objectives Related to Safety: Other secondary safety objectives include evaluation of the incidences of the following:
 
 1. bleeding that does not meet the TIMI criteria for major or minor (i.e., minimal bleeding); 2. “clinically significant” bleeding; 3. TIMI bleeding related to coronary artery bypass grafting (CABG); and 
Other Secondary Objectives Related to Efficacy: Other secondary efficacy objectives will include evaluation of the following:
 
 1. incidence of the individual components of the MACE composite as measures of potential clinical benefit; 2. incidence of definite or probable stent thrombosis as a measure of potential clinical benefit; 3. inhibition of platelet aggregation induced by SFLLRN (PAR1 agonist) and thrombin as an indicator of the desired pharmacodynamic effect, and ADP (adenosine diphosphate), collagen and AYPGKF (PAR4 agonist) to evaluate the specificity of PZ-128; 4. effect of the investigator choice of P2Y₁₂ inhibitor on the individual components of the MACE composite; and 5. population pharmacokinetics. 
Exploratory Objectives: Exploratory objectives will include the following:
 
 1. incidence of bleeding events according to the BARC (Bleeding Academic Research Consortium) classification; 2. effect on expression of systemic markers of thrombosis and platelet reactivity, inflammation, and metabolomics; and 3. population pharmacogenomics. 	

Methodology: Multicenter, prospective, randomized, double-blind, placebo-controlled, balanced-parallel-groups, non-inferiority investigation.

Number of Subjects (planned): Approximately 600 (400 to receive PZ-128, 200 to receive placebo). There is no pre-specified minimum or maximum enrollment for each site.

Diagnosis and Main Criteria for Inclusion: Adult subjects (≥ 18 years), meeting all inclusion criteria and none of the exclusion criteria, scheduled to undergo non-emergent coronary angiography +/- PCI (if indicated) for either stable coronary artery disease or non-ST-segment elevation acute coronary syndromes (NSTE-ACS) (i.e., candidates for elective or urgent PCI), and for whom elective use of a GP IIb/IIIa inhibitor (GPI) is not intended, will be enrolled.

Investigational Product, Dose and Mode of Administration: PZ-128 lyophilized powder for reconstitution in Sterile Water for Injection and dilution in 5% Dextrose. Subjects receive 0.3 mg/kg or 0.5 mg/kg as a single-dose via a continuous, 2-hour, intravenous infusion.

Reference therapy, Dose and Mode of Administration: Matching placebo lyophilized powder for reconstitution in Sterile Water for Injection and dilution in 5% Dextrose. Subjects receive placebo corresponding to PZ-128 0.3 mg/kg or 0.5 mg/kg as a single-dose via a continuous, 2-hour, intravenous infusion.

Duration of Treatment: Single dose infusion to start within one hour before the diagnostic angiography begins. Subjects are expected to receive the entire 2-hour infusion regardless of whether they proceed to undergo PCI, CABG or medical management.

Criteria for Evaluation

Primary Safety Endpoint: The primary safety endpoint of the study will be the incidence of TIMI major plus minor bleeding not related to CABG through 30 days after treatment. TIMI Major bleeding is defined as (1) intracranial hemorrhage or (2) clinically significant overt signs of bleeding associated with a decrease in hemoglobin concentration of ≥ 5 g/dL (or hematocrit $\geq 15\%$) or (3) fatal bleeding within 7 days. TIMI Minor bleeding is defined as clinically overt signs of bleeding (including imaging) associated with a decrease in hemoglobin concentration of 3 to < 5 g/dL (or hematocrit of 9 to $< 15\%$) that does not otherwise meet criteria for major bleeding. Hemoglobin concentration and hematocrit will be adjusted for any transfusion of packed red blood cells or whole blood given between enrollment and post-transfusion measurements.

Key Secondary Efficacy Endpoint: The key secondary efficacy endpoint is the incidence of any component of the MACE composite through 30 days and 90 days after treatment.

Other Secondary Endpoints Related to Safety: Other secondary safety endpoints include the incidences of the following:

1. TIMI minimal bleeding not related to CABG (defined as clinically significant overt signs of bleeding associated with a drop in hemoglobin concentration of < 3 g/dL (or hematocrit of $< 9\%$) that does not otherwise meet criteria for major or minor bleeding) through 30 days after treatment;
2. "clinically significant" bleeding (defined as TIMI major or minor bleeding or bleeding requiring medical attention) through 30 days after treatment;
3. TIMI bleeding related to CABG through 30 days after treatment (subjects who undergo CABG will specifically have assessment of (a) surgical wound bleeding using quantitative total chest tube drainage in the first 24 hours; (b) need for transfusion of blood products in the first 48 hours; and (c) need for surgical re-exploration).

Other Secondary Endpoints Related to Efficacy: Other secondary efficacy endpoints will include the following:

1. incidence of the individual components of the MACE composite through 30 days and 90 days after treatment;

2. incidence of definite or probable stent thrombosis through 30 days and 90 days after treatment;
3. inhibition of platelet aggregation induced by SFLLRN, thrombin, ADP, collagen and AYPGKF, relative to baseline at several time points following treatment at select sites;
4. population pharmacokinetics at baseline and at several time points following treatment; and
5. effect of the investigator choice of P2Y₁₂ inhibitor (i.e., clopidogrel versus prasugrel/ticagrelor) on the individual components of the MACE composite.

Exploratory Endpoints: These endpoints are not part of the formal objectives and are included as additional ways to evaluate bleeding and to gather information for future research.

1. incidence of bleeding events according to the BARC (Bleeding Academic Research Consortium) classification through 30 days after treatment;
2. change from baseline in select systemic markers of thrombosis and platelet reactivity, inflammation, and metabolomics at select time points;
3. population pharmacogenomics at baseline.

Clinical evaluations including physical examinations, vital signs, laboratory tests, electrocardiograms and the assessment of adverse events will be performed for all subjects during hospitalization and at follow-up time points as measures of the safety profile.

Randomization: Randomization will be conducted prior to the diagnostic angiography.

Stratification: Randomized assignment of PZ-128 and placebo will be stratified for whether the cardiac catheterization ± PCI is being done on an elective or urgent basis at the time the operator decides to perform the procedure.

Sample Size/Power: The current design anticipates a sample size of 600 subjects who will undergo non-emergent cardiac catheterization ± PCI. The sponsor anticipates that the incidence of major plus minor bleeding among placebo-treated subjects will range from 2% to 6% on the basis of historical experience. Given the anticipated sample sizes and estimated range of incidences associated with placebo, the study will be able to demonstrate that the bleeding risk of PZ-128 is non-inferior to the risk associated with placebo with non-inferiority margins in the range of 2.6 to 7.6%, depending on the underlying bleeding risk of placebo. Given the anticipated benefits of PZ-128, these non-inferiority margins are reasonable for the planned safety decisions generated from this trial.

Statistical Methods: All subjects who are randomized will be considered evaluable for the analyses. The following statistical analysis will be provided for the primary endpoint. The point estimate of the difference in risk of any event of non-CABG TIMI major plus minor bleeding through 30 days post treatment for between PZ-128 and placebo (e.g., Pr (Event in PZ-128 patient)-Pr (Event in placebo patient)), and corresponding lower one-sided 95% confidence interval will be presented. These estimates will be generated using subjects who underwent diagnostic angiography for all PZ-128 treatment arms pooled across both doses (~400 subjects) and all placebo (~200 subjects) and descriptive results will also be generated for each individual dose. The proposed phase 2 study is not of sufficient size or of sufficient follow-up duration to allow formal analysis of clinical efficacy.

Sub-analyses of the endpoints will be performed across subject cohorts (i.e., PCI, CABG and medical management). Comparisons for primary and secondary endpoints will be done for PZ-128 in aggregate and per dosing group. The potential influence of baseline risk factors and concomitant therapies such as statins, choice of P2Y₁₂, and aspirin dosing on the incidences of the endpoints will also be explored using generalized linear models and survival models.

[figure not shown]
Subgroup analyses will be conducted for baseline characteristic variables such as age, sex, and race. All bleeding events will be characterized as non-CABG or CABG related and the following bleeding rates will be reported: total, CABG-related and non-CABG-related.

Tabulations of descriptive statistics will be provided for TIMI major plus minor bleeding. In addition, tabulations of descriptive statistics will also be provided on the incidence of all other relevant variables.

Although no formal stopping boundaries will be utilized, one interim safety analysis will be performed at approximately one year following the enrollment of the first subject, or after enrollment of 50% of the study population, whichever occurs first. The Data and Safety Monitoring Board (DSMB) will be provided point and interval estimates of PZ-128 benefit at the time of that analysis based on survival estimates, and will evaluate evidence of bleeding risk in light of the potential efficacy benefits in making recommendations about stopping the trial.

Among the committees formed to oversee the conduct of the study will be an independent DSMB to protect further the rights, safety and well-being of subjects who will be participating in this study by monitoring the progress and results of the trial, and an independent Clinical Events Committee (CEC) to review and adjudicate each suspected bleeding and efficacy endpoint event while blinded to treatment.

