6.2 Participation in and Completion of the Study

The subject is considered to be enrolled in the study when the subject is successfully randomized and is assigned a study drug treatment regimen and a unique subject randomization number. A subject who receives a randomization assignment without ever receiving any amount of study drug treatment (“randomized but not treated”) is still part of the intent-to-treat (ITT) data set for efficacy endpoints and must be followed thereafter per protocol (a telephone contact may be used in lieu of the 14-day follow-up visit for those not having taken any amount of study drug). A subject who signs the informed consent to participate in the study but does not undergo a successful randomization (i.e., screen failure, withdrew consent) will not be followed beyond the point it is determined that the subject will not be randomized- no further data will be collected and the subject will not be included in safety or efficacy analyses. Information on subjects who are screened and consented for the study but fail to undergo randomization will be submitted to the sponsor as per **Section 8.2** for regulatory purposes and to establish that the study population was selected without bias.

The subject is considered to have completed the study drug treatment following cessation of the study drug infusion. Given the single-dose design of the study, once the subject has received the study drug infusion (or once a subject permanently discontinues the study drug infusion), the study drug will no longer be available to the subject.

The subject is considered to have completed the entire study when he/she has undergone the final protocol-specified contact (i.e., study telephone call at 90-days following the study drug administration). Subject participation may be terminated prior to completion for reasons described in **Section 6.3.3**. For those subjects who do not complete the entire study protocol, subject participation will be considered terminated upon the completion of the last visit or phone contact.

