6.4.1 Blinded Investigational Study Drugs

Approximately 600 subjects will be randomized in a 2:1 (PZ-128: PZ-128 placebo) ratio to receive 1 of the following 4 treatment assignments:

- Single, 2-h IV infusion of PZ-128 0.3 mg/kg
- Single, 2-h IV infusion of PZ-128 0.5 mg/kg
- Single, 2-h IV infusion of Placebo 0.3 mg/kg
- Single, 2-h IV infusion of Placebo 0.5 mg/kg

The PZ-128 active drug and matching placebo are provided as vials of solid lyophilized powder cake for reconstitution and will be indistinguishable. The individualized dose will be based upon the baseline (i.e., Screening) weight of the subject and the dose level assignment by the centralized randomization system used as part of the method of treatment assignment (**Section 6.4.4**). The type and number of vials of study drug will be selected by an unblinded investigational pharmacist (**Section 6.4.6**) at the clinical site who is able to obtain the subject's unmasked randomized treatment assignment via a restricted access login within the randomization system. Each vial of study drug will be reconstituted with 10 mL of Sterile Water for Injection, USP (SWFI) and the calculated amount of reconstituted volume of study drug will be mixed and diluted with 250 mL (plus the manufacturer's overfill volume) of Dextrose 5% in Water, USP (D5W) to yield a final IV bag (blinded) for administration.

PZ-128 or matching placebo, as determined by the randomization scheme, will be administered by a qualified member of the study staff or institution's clinical staff over a 2-hour continuous IV infusion and the infusion must begin 0-60 min prior to the start of the cardiac catheterization (i.e., diagnostic coronary angiography). The infusion will run through completion regardless of whether the subject progresses to PCI, CABG or medical management.

[REDACTED] The peripheral IV line for the drug infusion should not be smaller than 20-gauge. Flushing of the IV access site (not the line) will be done using 0.9% Sodium Chloride for Injection (Normal Saline).

[REDACTED]

[REDACTED]

[REDACTED]

[REDACTED]

[REDACTED]

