Based on the judgment of the investigator or qualified designee (i.e., enrolling/treating sub-investigator), dosing with the study drug may be withheld, interrupted and/or discontinued for any clinical situation in order to preserve the protection, safety and well-being of the subject.

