7.3 Data Sets

Safety analysis set

Safety evaluations will include subjects who have been randomized and who have received any amount of study drug treatment. Subjects will be evaluated according to treatment actually received. The safety analysis set will be used as the primary analysis dataset for the reporting of both the primary and secondary safety analyses as described below.

Intention-to-treat analysis set

Efficacy analyses will be carried out on an intent-to-treat basis, and all evaluations will include all subjects who receive randomization assignment, irrespective of initiation of treatment, who provide at least one outcome assessment. Subjects will be analyzed according to the assigned study treatment irrespective of any treatment allocation errors.

Per-protocol analysis sets

Per-protocol analysis sets will also be defined during the masked review for total bleeding events, and key efficacy outcome measures. Subjects will be excluded from the per protocol analysis sets as a result of protocol deviations likely to influence the outcome variables (exact details of possible protocol deviations will be detailed in the SAP). Similar conclusions from both the safety analysis set and per protocol analysis set are required for a robust interpretation of the bleeding event results.

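### The synopsis and Section 7.3 name different populations for the primary bleeding estimate, and the synopsis words its one-sided interval ambiguously

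*Combined protocol and SAP*

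**What the plan says.** **Population.** The Statistical Methods paragraph of the synopsis opens with a general statement: "All subjects who are randomized will be considered evaluable for the analyses". It then specifies the primary analysis, a risk difference in non-CABG TIMI major plus minor bleeding to 30 days, and says: "These estimates will be generated using subjects who underwent diagnostic angiography", with about 400 on PZ-128 and about 200 on placebo. The synopsis paragraph on sample size says: "The current design anticipates a sample size of 600 subjects who will undergo non-emergent cardiac catheterization".

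Section 7.3 defines the safety analysis set as randomised subjects given any study drug, grouped by the treatment they actually got, and adds: "The safety analysis set will be used as the primary analysis dataset for the reporting of both the primary and secondary safety analyses". It sets no angiography condition. Section 6.2 says that a subject who is randomised but never treated "is still part of the intent-to-treat (ITT) data set for efficacy endpoints".

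**Interval.** The synopsis defines the difference as PZ-128 minus placebo and says that the "corresponding lower one-sided 95% confidence interval will be presented". Section 7.5.4 states the hypothesis that this difference lies below a margin and calls for a one-sided 95% interval without naming a side. Section 7.7 bases the non-inferiority margin on the upper limit of the interval already defined.

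**The concern.** Both points concern the primary analysis. An analyst working from the synopsis would select subjects on an event that comes after treatment has begun; one working from Section 7.3 would not. Nothing in the document says that the body overrides the synopsis, so the choice of who enters the primary estimate is left open.

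On the interval, a positive difference means more bleeding on PZ-128. To conclude that the excess is smaller than a margin, one must bound it from above. A lower limit answers a different question, namely whether there is evidence of some excess. If the synopsis were followed on its plain reading, the reported limit would not address the hypothesis in Section 7.5.4.

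**Working it through.** **1. Can the two populations differ?** Section 6.4.1 requires that "the infusion must begin 0-60 min prior to the start of the cardiac catheterization", so treatment starts before angiography. Section 6.4.7.7 says that "dosing with the study drug may be withheld, interrupted and/or discontinued for any clinical situation". This gives four cases:

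| Subject | Safety set (7.3) | Angiography set (synopsis) |
|---|---|---|
| Treated, angiography done | in | in |
| Treated, angiography not reached | in | out |
| Drug withheld, angiography done | out | in |
| Neither | out | out |

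Neither set contains the other.

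**2. How much could it matter?** The documents give no count for the two middle rows. The synopsis expects about 400 and 200 catheterised subjects, the same as the randomised totals, so discordance is probably rare.

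As an assumption only, take 24/400 bleeds on PZ-128 and 8/200 on placebo. These are 6% and 4%, a point on the Section 7.7 grid. Let 2% or 5% of each arm be treated but not reach angiography. The upper limit is d + 1.645 × SE, with SE = √[pT(1−pT)/nT + pC(1−pC)/nC].

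| Excluded | Bleeds lost | Difference (points) | Upper limit (points) |
|---|---|---|---|
| none | none | 2.00 | 5.00 |
| 2% (392/196) | 2 on PZ-128 | 1.53 | 4.54 |
| 2% (392/196) | 1 on placebo | 2.55 | 5.50 |
| 5% (380/190) | none | 2.11 | 5.26 |
| 5% (380/190) | 1 on PZ-128 | 1.84 | 4.97 |
| 5% (380/190) | 2 on PZ-128 | 1.58 | 4.68 |
| 5% (380/190) | 1 on placebo | 2.63 | 5.68 |

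The upper limit moves by between -0.46 and +0.68 points, and the direction depends on whose bleeds drop out. These cases show scale; they do not predict or bound the effect.

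**3. Which limit tests the hypothesis?** Inputs from Section 7.7: 400 and 200 subjects, placebo risk 2% to 6%, true difference 0 to 2 points. The one-sided 95% level is from Section 7.5.4, so z = 1.645.

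The plan's own figure first. At 4% placebo risk and zero difference, Section 7.7 states a margin of 3.7%. SE = √(0.0384/400 + 0.0384/200) = 1.697 points. With 80% power the margin would be (1.645 + 0.842) × 1.697 = 4.22 points, so the stated figure does not reproduce on this formula. That is a separate matter: only the inputs of Section 7.7 are used here.

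Expected unadjusted Wald limits:

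- 4% in both arms: 0 ± 1.645 × 1.697 gives -2.79 and +2.79 points.
- 6% on PZ-128 and 4% on placebo: SE = √(0.0564/400 + 0.0384/200) = 1.825, so 2 ± 3.00 gives -1.00 and +5.00 points.
- Whole grid: lower limit -3.38 to -0.29; upper limit 1.99 to 5.55.

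The expected lower limit is negative throughout, so it lies below any positive margin whatever the margin is. Only the upper limit is informative about non-inferiority. The adjusted model in Section 7.5.4 may give somewhat different values.

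**The case against.** The strongest reply is that Section 7 already answers both questions. Section 7.3 names the population. Section 7.7 refers back to an interval defined earlier, and the only such interval in Section 7 is the one-sided one in Section 7.5.4. Read together with the stated hypothesis, these sections fix the upper limit. The synopsis phrase can also be read as an interval open below and bounded above, which agrees with them. This stands: the interval problem is one ambiguous synopsis phrase, and the edit to Section 7.5.4 is for clarity.

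The angiography wording may be meant only to say that everyone catheterised counts, not just those who had PCI. That fits the expected 600 catheterised subjects, but the synopsis does not say it. The room for discordance is also narrow: Section 6.4.5 allows no start outside the pre-angiography window, and Section 6.3.4 lets untreated subjects who discontinue be replaced. Section 7.3 further asks for similar conclusions from a per-protocol set, and Section 7.2 leaves further detail to an SAP written before unmasking. These limit the likely effect, but they do not remove the conflict between the synopsis and Section 7.3.

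A reader might infer that the plan names three populations for the primary endpoint, counting all randomised subjects as the third. The documents do not support that. The sentence on evaluability is general and comes before the primary-endpoint specification, and Sections 6.2 and 7.3 tie the randomised set to efficacy.

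**Conclusion.** The concern holds as an internal inconsistency of low to moderate severity. On population the conflict is real: angiography subjects in the synopsis, the safety analysis set in Section 7.3. The sets can differ in both directions. The effect is probably small, an inference from the expected near-complete catheterisation. Its size and direction cannot be fixed from the documents.

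On the interval, the synopsis wording is ambiguous and, on its plain reading, names the wrong side. A reader might go further and infer that the trial could declare PZ-128 acceptable by comparing a lower limit with a margin, and so tolerate a large excess of bleeding. No section states such a rule. The synopsis says only that the interval will be presented. The margins in Section 7.7 are the smallest demonstrable at the planned power, and Section 7.5.4 lets the acceptable margin depend partly on efficacy.

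The limits quoted rest on unadjusted Wald calculations with 400 and 200 subjects. The logical point does not depend on them.

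**What to change.** In the synopsis, name the Section 7.3 safety analysis set as the single primary population for bleeding, and label any angiography-only result descriptive. Replace the interval phrase with *upper one-sided 95% confidence limit*, and use the same words in Section 7.5.4. This follows what Sections 7.3 and 7.7 already say. The cost is a wording change in the synopsis and one sentence of Section 7.5.4, with no added analysis or data. It should be made before unmasking so that the SAP has one text to follow.
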